#### 5.2 Study Procedures:

Voice assessment. To assess voice quality, participants will perform two voice production tasks. First, they will vocalize the vowels 'ahh' and 'ee'. They will perform each task three times per assessment. Second, they read aloud twenty test sentences. They will repeat these assessments several times during testing (see Fig. 4). The sentence reading task consists of a set of test sentences based on a 20-sentence inventory described by Ludlow et al. as being sensitive to the voice symptoms experienced in SD [2]. Participants will read the sentences at their own comfortable pace and loudness. In addition, participants will rate their perceived effort level of vocalization on an ordinal scale of 0 to 10 (0 being with no effort and 10 being with maximal effort).

Application of laryngeal vibration. Each VTS trial begins with a 10-second rest period, followed by 4 seconds of vocalization. After 2 seconds of vocalization, vibration will set in while the subject continues to vocalize. Thus, each trial has a rest, a vocalization only, and a vocalization + vibration period. Each participant performs 50 trials per set. The timeline of the complete protocol is illustrated in Figure 4. Testing will begin with a pretest voice assessment, followed by two sets comprising the vibration only and vocalization + vibration conditions. The order of the conditions will be counter-balanced between subjects to account for possible order effects. During the vibration only condition, subjects will be silent and are allowed to read for diversion. After each set a 5-min break will be given and fluids will be offered. Voice assessment batteries will be administered after each set. After completion of two sets and final voice assessments are immediately after treatment (Post 2 OFF), and 20 min and 60 min after VTS has stopped (Post 20, Post 60).

Page 13 of 27

Revised: 9/28/2017

#### Deleted: 4

PROTOCOL TITLE: Effect of Short-term Laryngeal Vibration on Voice Quality. Grant title: Feasibility of laryngeal vibration as a treatment for spasmodic dysphonia 01/31/2021

Figure 2 Experimental design for in-person testing.

Usability questionnaire: The last section of study is to ask participants to fill out a questionnaire about the usability of the wearable collar.

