#### **10.0** Local Number of Participants

10.1 Local Number of Participants to be Consented:

Number of patients with spasmodic dysphonia (SD) will be 20 and number of healthy control subjects (CTL) are 20.

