#### 15.0 Statistical Considerations

#### 15.1 Data Analysis Plan:

Analysis of voice data. Acoustic analysis will follow the methodology described by [50]. Waveform and wide-band spectrograms will be used to identify and measure the duration of the variables. The acoustic signal will be examined for the presence of phonatory breaks and aperiodic breaks. Phonatory breaks are defined as any voiced phonemic segment without sound that is greater than 50ms; the duration of phonatory breaks will be measured. Aperiodic segments will be identified as any voiced phonemic segment that contains non-repetitive cycles that are greater than 50ms; and the duration of the break will be measured. To standardize the duration measures for both phonatory and aperiodic breaks, the sum of the duration of breaks will be divided by the sum of the duration of all voiced segments for each subject. Inter-rater reliability will be measured using Cohen's alpha and intra-rater reliability will use Pearson's r correlation (expected to range between r=.89 to r= .98 according to [50]). For both break types, the absence of phonation or the presence of aperiodicity at the boundary of a syllable or the beginning of a word will not be considered. We will perform a MANCOVA procedure employing all acoustic variables with pre-/posttests as independent factors. If the MANCOVA is significant, separate univariate ANOVAs will be performed on each acoustic variable (dependent) and assessment conditions as a repeated measure (independent) [50]. Appropriate Bonferroni adjustments will account for multiple testing.

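### Section 15.1 plans Bonferroni for the acoustic tests, which is valid; Holm's step-down version holds the same error rate, never rejects less, and gains power for second and later rejections.

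*Combined protocol and SAP*

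**What the plan says.** The voice analysis in section 15.1 has three steps.

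- A global test: "We will perform a MANCOVA procedure employing all acoustic variables with pre-/posttests as independent factors".
- A gate and follow-up. "If the MANCOVA is significant", then "separate univariate ANOVAs will be performed on each acoustic variable (dependent) and assessment conditions as a repeated measure (independent").
- The adjustment: "Appropriate Bonferroni adjustments will account for multiple testing".

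Two acoustic variables are named: "The acoustic signal will be examined for the presence of phonatory breaks and aperiodic breaks". For the timing, section 5.2 says "Voice assessment batteries will be administered after each set" and adds that "final voice assessments are immediately after treatment (Post 2 OFF), and 20 min and 60 min after VTS has stopped (Post 20, Post 60"). Section 10.1 gives the numbers: "Number of patients with spasmodic dysphonia (SD) will be 20 and number of healthy control subjects (CTL) are 20".

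The protocol states no significance level, no sidedness, no number of tests and no list of time-point contrasts. It does not say whether the Bonferroni adjustment is single-step or step-down. It contains no power calculation.

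**The concern.** Single-step Bonferroni compares every p-value with α/m. Holm compares the smallest p-value with α/m, the next with α/(m−1), and so on, stopping at the first failure. If vibration works, several comparisons may move together: two break ratios, each assessed after the sets and again at 20 and 60 minutes. Whether an effect persists is a question about several rejections, not just one. With 20 patients, a rule that holds every test to the strictest threshold gives up some power for the later rejections, and Holm recovers that power without weakening error control.

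**Working it through.** **Inputs from the protocol.** 20 patients with spasmodic dysphonia (section 10.1); two named break measures (15.1); a pretest and repeated post-vibration assessments (5.2). There is no planned power or adjusted level to reproduce.

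**Assumptions.** Two-sided α = 0.05; paired pretest-versus-post t-tests with 19 df; standardised change d of 0.6, 0.7 or 0.8. The family size m is unknown, so a range is shown: m = 2 (the two break ratios) and m = 8 (two ratios × four post-vibration assessments). Correlation for m = 8 is 0.5 across time and 0.3 across variables. The MANCOVA gate is not modelled.

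**1. Error control.** Bonferroni is valid. For independent tests the family-wise error is 1 − (1 − 0.05/m)^m, which gives 0.0494 (m = 2), 0.0491 (m = 4) and 0.0489 (m = 8). For Holm, let m₀ be the number of true nulls. When the first true null is tested, at least m₀ hypotheses remain, so its threshold is at most α/m₀. By Bonferroni's inequality the error is at most m₀ × α/m₀ = α, whatever the dependence.

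**2. Never fewer rejections.** Holm's j-th threshold is α/(m − j + 1), which is at least α/m. For m = 2 the thresholds are 0.025 and 0.05. For m = 8 they run 0.00625, 0.00714, 0.00833, 0.01, 0.0125, 0.0167, 0.025, 0.05. Any p-value that passes α/m also passes Holm. The first threshold is the same, so the chance of at least one rejection in the family is identical.

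**3. Single-step power per test at d = 0.7.** The noncentrality is 0.7 × √20 = 3.13.
- m = 2: level 0.025, critical t 2.433, power 75%.
- m = 8: level 0.00625, critical t 3.074, power 54%.

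**4. Bonferroni against Holm, by simulation** (at least 20,000 replicates per case). The figures are average power over the real effects.

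| Family | Real effects | d | Bonferroni | Holm |
|---|---|---|---|---|
| 2 | both | 0.7 | 75% | 81% |
| 8 | all 8 | 0.6 | 38% | 48% |
| 8 | all 8 | 0.7 | 54% | 68% |
| 8 | all 8 | 0.8 | 69% | 83% |
| 8 | 4 | 0.6 | 38% | 41% |
| 8 | 4 | 0.8 | 69% | 73% |
| 8 | 2 | 0.7 | 53.7% | 54.9% |
| 8 | 1 | 0.7 | 53.7% | 53.8% |

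The m = 2 row uses a correlation of 0.3 to 0.5 between the two ratios.

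**5. Other measures.** With all eight real, the chance of at least one rejection is the same under both rules: 88.2% at d = 0.6 and 96.0% at d = 0.7. The chance of rejecting all eight at d = 0.7 rises from 6–8% to 36–39%, depending on how the correlations across variables are laid out. With four of eight real, Holm's family-wise error stays at 3–4%.

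**The case against.** The strongest reply is that this is a preference. Single-step Bonferroni is valid, no statement in the protocol is false, and the same remark could be made about almost any plan that names Bonferroni. That stands, and it sets the weight of the point.

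Four further objections stand in part.

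- **Wording.** The protocol does not say single-step. That is the natural reading, but the step-down form is not excluded. If it was intended, naming it costs nothing.
- **Family.** Eight comparisons is an assumption. Section 15.1 describes one repeated-measures ANOVA per variable and lists no pretest-versus-post contrasts, so the family may be only two. The gain is then about 6 points rather than 14, even if both effects are real.
- **Gate.** The univariate tests run only after a significant MANCOVA, so the absolute powers above are not those of the full procedure. The gate precedes either adjustment, so Holm still rejects no less. If the family were just two variables and the MANCOVA a valid global test of both, closed testing would allow each to be tested at full α, and Holm would not be the natural benchmark.
- **Intervals.** Bonferroni gives simple simultaneous confidence intervals and Holm does not. For a study seeking preliminary data in a limited sample, intervals matter at least as much as extra rejections.

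A reader might infer that power is being thrown away at no cost, or that real retention effects will be missed. The documents support neither. Detection of at least one effect is unaffected, the interval cost is real, and the large gains require many true effects of similar size. If the effect fades by 20 or 60 minutes, the study lies nearer the rows with few real effects, where the gain is small.

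**Conclusion.** The point holds as an optional, low-cost gain in efficiency. Under the stated assumptions, Holm adds about 6 points of average power if the family is the two break ratios and both change, and about 14 points if all of eight equal effects are real (d = 0.7). It adds about 3 to 4 points if four of eight are real (d = 0.6 and 0.8), and about 0 to 1 point if one or two are. Error control and the dominance over single-step Bonferroni need none of these assumptions. The sizes do, because the protocol gives no level, family or effect size.

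No planned conclusion becomes invalid if Bonferroni is kept. The more basic gap in the same sentence is that the level and the family are undefined, so neither method can yet be applied as pre-specified.

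**What to change.** In section 15.1, replace the Bonferroni sentence with:

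> After a significant MANCOVA, Holm step-down adjustment at two-sided 5% is applied over the planned pretest-versus-post comparisons of all acoustic variables [list the variables and time points]; Holm-adjusted p-values are reported.

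The list in brackets matters as much as the change of method, because it fixes m. Beside the adjusted p-values, show Bonferroni or unadjusted confidence intervals, labelled as such. They will not always agree with the Holm decisions, and the text should say so. The cost is one sentence and one short list; no data collection or sample size changes.

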#### 5.0 Procedures Involved

#### 5.1 Study Design:

Subjects will perform voice production tasks before, during and after vibration. The subject will wear the collar around their neck. Two lightweight, low voltage, non-invasive surface electrical vibratory motors that are embedded in the wearable collar will be positioned on the skin of the anterior portion of the neck adjacent to the voice box to vibrate the larynx (see Fig. 3 for demonstrating the location of vibrators). Voice production before, during, and after the vibration will be recorded via a microphone for subsequent acoustic analysis on voice quality by speech analysis experts. In addition, during voice production, electroencephalography (EEG) will be recorded with a 64-channel system (Active 2 BioSemi B.V., Amsterdam, The Netherlands or the mobile ANT Neuro EEGO EEG System, Hengelo, The Netherlands) at a sampling frequency of 512 Hz. Subjects will wear a regular head cap arranged in the standard 10-20 configuration (see Figure 1). Four additional external electrodes will be used. Two electrodes will be placed above and below the left eye to detect eye movements. Another two electrodes will be attached on bilateral mastoid processes to serve as reference electrodes. A water-based conductive gel is applied between the electrodes and the skin, which can be cleaned easily with water.

Deleted: Figure 1

Page 12 of 27

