Analysis of EEG data. EEG recordings during speech are known to be susceptible to noise from the multiple muscles in and near the head that are involved in speech production. We have been cognizant to this fact and a) designed a simple vocalization task that does not involve complex patterns of muscle activation and b) use modern noise removal techniques that have been successfully applied for the analysis of voice related EEG. [name] is an expert in the analysis of speech-related EEG and will lend his expertise for EEG data analysis, which is based on the widely utilized MATLAB EEGlab toolbox [51]. Space limitation does not permit to describe all processing steps in detail. However, here we outline its major approach. First, to remove motion and electromyographic artifacts, all channels will be filtered (0.5 Hz high-pass and 20 Hz low-pass FIR filter). Second, target events will be extracted and trials containing non-physiological signal amplitudes will be rejected (typically outside [-100 µv 100 µv]). Third, for further objective noise removal the ADJUST algorithm (Automatic EEG artifact Detector based on the Joint Use of Spatial and Temporal features)

Page 20 of 27

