will be utilized - algorithm also included in the NIH Neuroimaging Tools and Resources Platform. Finally, an Independent Component Analysis (ICA) will be applied [52]. The ICA statistically decomposes all 64 channels into 64 independent sources of information (components) whose weighted sum is assumed to result in the formation of the recorded data. After this step, the pruned components are combined, generating a cleaner data set. After the ICA weights have been computed, the ADJUST will be employed to detect those independent components, which based on the statistical criteria of the algorithm, were the potential sources of stereotyped artifacts (eye blinks, vertical eye movement, horizontal eye movement, generic discontinuity i.e. inappropriate signals due to noisy channels or muscle activation) [53]. The statistical criteria for removing noise components include temporal kurtosis and spatial average difference [SAD] (from eye blinking), the maximum epoch variance [MEV] and SAD (from vertical eye movements), the MEV and spatial eye difference [SED] (from horizontal eye movements), and MEV and the generic discontinuity spatial feature [GDSF] (from bad channels and muscle activation). After the removal of noise components, a time-frequency analysis will be carried out on all channels of the pruned dataset. The analysis will yield the mean eventrelated changes in the spectral power "ERSP" (from pre-stimulus baseline) for the different frequency ranges at each time instance of all epochs.

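### The EEG plan rejects trials on a fixed amplitude limit before the ICA/ADJUST step meant to correct blinks, so correctable trials may be lost

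*Combined protocol and SAP*

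**What the plan says.** The EEG part of section 15.1 (Data Analysis Plan) numbers its steps.

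- **First**, filtering: "all channels will be filtered (0.5 Hz high-pass and 20 Hz low-pass FIR filter".
- **Second**, amplitude rejection: "Second, target events will be extracted and trials containing non-physiological signal amplitudes will be rejected". The limit given is typically -100 to +100 µV.
- **Third**: "Third, for further objective noise removal the ADJUST algorithm" is introduced.
- **Last**: "Finally, an Independent Component Analysis (ICA) will be applied".

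A later sentence in the same section reverses the last two: "After the ICA weights have been computed, the ADJUST will be employed to detect those independent components". The components it looks for are those that "were the potential sources of stereotyped artifacts (eye blinks, vertical eye movement, horizontal eye movement", together with discontinuities from noisy channels or muscle activity. The cleaned data then go into a time-frequency analysis whose output is the mean ERSP over epochs.

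Section 5.1 adds external electrodes to the 64-channel cap: "Two electrodes will be placed above and below the left eye to detect eye movements". Section 5.2 gives 50 trials per set, each with 10 s of rest and 4 s of vocalization. The plan does not say which channels or what time window the amplitude limit covers, whether the limit is applied again after component removal, or how many trials must remain.

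**The concern.** Blinks and eye movements are what the ICA/ADJUST step exists to correct, and they can also push a trial past a fixed amplitude limit. If the limit acts first, the affected trial is gone before the correction runs. ICA then also sees fewer examples of the artifacts it has to separate.

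What is at stake is the precision of each participant's ERSP, which is an average over the retained trials. The EEG is not incidental. Section 3.1 names cortical activity in SD and the cortical response to vibration among what the work should document, and section 1.1 lists the neural mechanism first among its scientific yields. The sample is 20 patients and 20 controls (section 10.1), and anyone tested remotely contributes no EEG.

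**Working it through.** **1. Order of steps.** The plan states no expected trial loss, so there is no figure to reproduce. The check is of sequence. Filtering is first and rejection second. The text is inconsistent about whether ADJUST or ICA comes next, but rejection precedes both under either reading. The text neither exempts ocular artifacts from the limit nor re-applies the limit later.

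**2. Does the filter already remove the problem?** The limit acts on 0.5-20 Hz data, so the question is how much of a blink survives. As an illustration, a Gaussian blink was passed through a 0.5 Hz high-pass and a 20 Hz low-pass FIR filter at 512 Hz (sampling rate from section 5.1). Blink widths and filter lengths are assumptions. The unfiltered peak needed to trip the limit is 100 divided by the share of the peak kept.

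| Blink width at half height (assumed) | Share of peak kept | Unfiltered peak that reaches 100 µV |
|---|---|---|
| 0.15 s | 0.841 | 119 µV |
| 0.20 s | 0.789 | 127 µV |
| 0.30 s | 0.689 | 145 µV |
| 0.40 s | 0.595 | 168 µV |

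The filter shrinks blinks without removing them. Under these assumptions, smaller blinks pass on to ICA/ADJUST as intended. Those above about 119-168 µV at a checked channel do not.

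**3. How many trials could be lost?** Let r be blinks per minute, q the share of blinks over the limit at a checked channel, and L the seconds checked per trial. If blinks arrive at random, the expected loss is 50 × [1 - exp(-r × q × L / 60)]. The 50 trials and the lengths of 4 s (vocalization) and 10 + 4 = 14 s (whole trial) come from section 5.2. The ranges r = 5 to 20 and q = 0.1 to 1.0 are assumptions. With a share p of trials lost, the standard error of a mean over trials grows by 1/√(1 - p), treating trials as independent and equally noisy.

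| L | r | q | r × q × L / 60 | Lost of 50 | Share lost | Standard error factor |
|---|---|---|---|---|---|---|
| 4 s | 5 | 0.1 | 0.033 | 1.6 | 3% | 1.02 |
| 4 s | 10 | 0.5 | 0.333 | 14.2 | 28% | 1.18 |
| 4 s | 20 | 1.0 | 1.333 | 36.8 | 74% | 1.95 |
| 14 s | 5 | 0.1 | 0.117 | 5.5 | 11% | 1.06 |
| 14 s | 10 | 0.5 | 1.167 | 34.4 | 69% | 1.79 |
| 14 s | 20 | 1.0 | 4.667 | 49.5 | 99% | 10.31 |

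The result runs from trivial to near-total. The inputs that decide it (blink rate, blink amplitude, channels and window checked) are all absent from the documents.

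**The case against.** The best defence is that the plan describes a sensible two-stage scheme. Gross artifact, which it calls non-physiological, goes first, and stereotyped artifact is left to ICA. Removing gross artifact before the decomposition is not in itself an error. The limit is only typically ±100 µV, and the section says that it is an outline that does not give every processing step.

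Much of this stands, but it does not close the gap. The only limit stated is a fixed amplitude, which cannot tell a gross movement artifact from a large blink, and nothing is said about checking again after cleaning.

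Four stronger readings are tempting, and the documents do not support them:

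- **Rejection on raw data.** It acts on filtered data, which lets smaller blinks through.
- **Correctable trials certainly discarded.** Only trials over the limit at a checked channel are affected. The documents do not show how many that would be.
- **A large loss is to be expected.** The near-total figures need a high blink rate, every blink over the limit, and the whole 14 s trial checked, rest included. The plan does not say that the whole trial is checked.
- **The group comparison is biased.** Nothing says that patients blink or move more than controls while voicing. The Background section mentions abnormal blink reflexes in SD, but that does not establish a higher blink rate. Section 5.2 lets participants read in the vibration-only set, but section 5.1 mentions EEG only during voice production. Section 15.1 also defines no between-group or between-condition EEG test. These are reasons to check retention, not evidence of bias.

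**Conclusion.** The point holds as a matter of order. Amplitude rejection precedes the step meant to correct blinks, eye movements and discontinuities, so trials with large but correctable artifacts may be lost. The consequence is a noisier mean ERSP. The loss cannot be determined from the documents; the ranges in the working rest on assumed blink shapes, rates and amplitudes and should not be quoted as expectations. Differential loss by group or condition remains a possibility to check.

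The reach is limited. The acoustic analysis, which serves the primary objective in the Study Summary, is untouched, and remote sessions have no EEG. This is a minor point, worth making because the remedy is specific and nearly free.

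**What to change.** Revise the EEG part of section 15.1 so that the steps read in this order:

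1. Filter as planned.
2. Before ICA, reject only gross, non-stereotyped artifacts, under a stated rule that an ordinary blink does not trip.
3. Run ICA, then ADJUST on the components. Reconcile the numbered list, which puts ADJUST third and ICA last, with the later sentence that runs ADJUST after ICA.
4. Remove the flagged components, rebuild the data, and apply the ±100 µV limit to the cleaned scalp channels over the analysed epoch. Name those channels and that epoch.
5. State a minimum number of retained trials, and report retained trials by group and condition.

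The change is offline. It needs no new data and adds nothing for participants. The cost is slightly more processing and inspection time.
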